10.5 Clinical Study Termination

If the clinical study is prematurely terminated or suspended, the Sponsor will inform the Investigator and the regulatory authorities of the termination/ suspension and the reason(s) for the termination/suspension. The Investigator should promptly notify the IEC/IRB of the termination or suspension and of the reasons. The Sponsor reserves the right to close the investigational site or terminate the study in its entirety at any time, for reasonable cause. Reasons for the closure of an investigational site or termination of a study may include:

- Successful completion of the study
- The study's enrollment goals are met
- The Investigator fails to comply with the protocol or GCP guidelines
- Safety concerns

- Sufficient data suggesting lack of efficacy
- Inadequate recruitment of subjects by the Investigator

The Investigator also may terminate the study at his/her site for reasonable cause. If the Sponsor terminates the study for safety reasons, it will immediately notify the Investigator(s) by telephone and subsequently will provide written confirmation of and instructions for study termination.

11 ANALYSIS PLAN

Continuous variables will be summarized for the observed values using the number of observations, mean, SD, median, minimum and maximum, as well as CIs or CLs where applicable. Categorical variables will be summarized with counts and percentages from each category. Any deviations to this analysis plan will be updated during the course of the study as part of a protocol amendment or will be detailed in the clinical study report.

11.1 Subject Evaluability

The final subject evaluability will be determined prior to breaking the code for masked lens care sequence assignment and locking the database.

11.2 Analysis Data Sets

11.2.1 Safety Analysis Set

Safety analyses will be conducted using the safety analysis set on a treatment-emergent basis. The safety analysis set will include all subjects/eyes exposed to the newly dispensed habitual lenses for the study disinfected with at least one study lens product evaluated in this study. For treatment-emergent safety analyses, subjects/eyes will be categorized under the actual lens care product exposed.

11.2.2 Full Analysis Set

The FAS is the set of all randomized subjects who are exposed to at least one of the study lens care products as defined for the Safety Analysis Set.

11.2.3 Per Protocol Analysis Set

The PP analysis set is a subset of all randomized subjects and excludes all data/subjects which have met any of the critical deviation criteria identified in the DEP.

11.3 Demographic and Baseline Characteristics

Demographic information (age, sex, ethnicity, and race) will be summarized on the safety, full, and PP analysis sets. Baseline characteristics on habitual lens and lens care information as well as activities, CLDEQ-8, [REDACTED], [REDACTED] [REDACTED] will be summarized on the full and PP analysis sets. Due to the crossover design, demographic and baseline data will be presented by lens care sequence group and overall.

11.4 Efficacy Analyses

This study defines one primary endpoint [REDACTED] All efficacy evaluations will use the FAS as the primary analysis set. [REDACTED]
[REDACTED]
[REDACTED]

For all planned inferential analyses, alternative models/methods may be considered if convergence cannot be achieved.

11.4.1 Primary Efficacy

The primary objective of this study is to demonstrate superiority of CCP when compared to habitual lens care product in reducing dryness symptomatology as measured by CLDEQ-8.

The corresponding endpoint is the score (range 0 to 37) from CLDEQ-8, obtained by adding the numerical responses to each of the 8 items, collected at the Day 30 follow-up, for each product (Visit 2 and Visit 3).

11.4.1.1 Statistical Hypotheses

The null and alternative hypotheses are formulated as follows:

$$H_0: \mu_{(CCP)} - \mu_{(HMPS)} \geq 0$$

$$H_a: \mu_{(CCP)} - \mu_{(HMPS)} < 0$$

where $\mu_{(CCP)}$ and $\mu_{(HMPS)}$ denote the mean CLDEQ-8 score for CCP and HMPS, respectively, at the Day 30 follow-up.

11.4.1.2 Analysis Methods

A mixed effect repeated measures model will be fit to test these hypotheses, including terms for lens care solution, period, sequence group, and baseline CLDEQ-8 as fixed effects and subject as a random effect. Lens care difference (CCP minus HMPS) and the corresponding one-sided 95% upper confidence limit will be provided.

Descriptive summary statistics will also be presented for the subgroup of habitual BIOTRUE formulation users.

11.4.2 Secondary Efficacy

[figure not shown]
No secondary efficacy objective is defined for this study.

[figure not shown]
11.4.2.1 Statistical Hypotheses

[figure not shown]
[figure not shown]
Not applicable.

11.4.2.2 Analysis Methods

Not applicable.

[figure not shown]

11.5 Handling of Missing Data

All data obtained in evaluable subjects/eyes will be included in the analysis. No imputation for missing values will be carried out for the efficacy analysis.

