5. A known sensitivity to any ingredients in CCP.
6. Biomicroscopy findings observed during the Visit 1 slit-lamp examination that are moderate (grade 3) or worse in either eye.
7. Prior refractive surgery (eg, laser assisted in situ keratomileusis [LASIK] and photorefractive keratectomy [PRK]).
8. History of herpetic keratitis, ocular surgery, or irregular cornea.

Sponsor:

Alcon Research, Ltd.
[name]

Protocol Number: LCS739-P001

9. A pathological dry eye that precludes contact lens wear.
10. Use of mechanical eyelid therapy or eyelid scrubs within 14 days before Visit 1 and not willing to discontinue during the study.
11. Enrollment of the Investigator or his/her staff, family members of the Investigator, family members of the Investigator's staff, or individuals living in the households of these individuals.
12. Enrollment of more than 1 member of the same household in the study.
13. Participation in any clinical study within 30 days of Visit 1.
14. Subjects who are currently using or have not discontinued Restasis®, Xiidra® or a topical steroid within the past 7 days.

Assessments:

- CL-induced dryness symptoms as measured by CLDEQ-8
- Symptomatology pre-screening questionnaire
- [REDACTED]
- [REDACTED]
- [REDACTED]
- [REDACTED]
- [REDACTED]
- [REDACTED]
- Biomicroscopy
- Snellen visual acuity
- AEs and device deficiencies

Statistical Methods:**Planned Analysis:**

Three analysis sets will be defined: safety, full, and per protocol (PP). The safety analysis set will include all subjects/eyes exposed to any

Sponsor:

Alcon Research, Ltd.
[name]

Protocol Number: LCS739-P001

[figure not shown]
study lens care products evaluated in this study. The full analysis set (FAS) is the set of all randomized subjects who are exposed to any study lens care products. The PP analysis set is a subset of all randomized subjects and excludes those who meet the critical deviation criteria as specified in the Deviations and Evaluability Plan (DEP). The FAS will serve as the primary analysis set for all efficacy evaluations.

All data from evaluable subjects will be included in the efficacy analysis; no imputation for missing values will be performed.

Efficacy:

To address the primary efficacy objective, planned analyses are summarized below.

Endpoint	Comparison	Statistical Method
PRIMARY		

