2.2 Full Analysis Set

The Full Analysis Set (FAS) will consist of all randomized subjects who are exposed to at least one of the study lens care products as defined for the Safety Analysis Set. Each subject will be classified according to the respective lens care products in the randomized lens sequence, irrespective of the exposure. FAS will serve as the primary analysis dataset for all efficacy evaluations.

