2.3 Per Protocol Analysis Set

The per-protocol (PP) analysis set is a subset of all randomized subjects and excludes all data/subjects which have met any of the critical deviation or evaluability criteria identified in the Deviations and Evaluability Plan. Each subject will be classified according to the respective lens care products in the randomized lens sequence, irrespective of the exposure.

3 Subject Characteristics and Study Conduct Summaries

Demographic information (age, sex, ethnicity, race) will be summarized on the safety, full, and PP analysis sets. Baseline characteristics on habitual lens and lens care information as well as activities, CLDEQ-8, [REDACTED], [REDACTED] [REDACTED] will be summarized on the full and PP analysis sets. Due to the crossover design, demographic and baseline data will be presented by lens care sequence group and overall.

All descriptive summary statistics will be displayed with n and % for categorical data, and with mean, standard deviation, median, minimum, and maximum for continuous data.

4 Efficacy Analysis Strategy

This study defines one primary endpoint [REDACTED] The Full Analysis Set will serve as the primary set for all efficacy analyses. [REDACTED]

[REDACTED]

[REDACTED]

[REDACTED]

[REDACTED]

[REDACTED]

[REDACTED]

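### Does the word 'evaluable' in the missing-data rule remove randomized, exposed subjects from the primary CLDEQ-8 test?

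*Protocol*

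**What the plan says.** Two protocol sentences describe which data enter the analysis, and both use the same undefined word.

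- Protocol 11.5: "All data obtained in evaluable subjects/eyes will be included in the analysis". The sentence that follows it says that missing efficacy values will not be imputed.
- Synopsis, Statistical Methods: "All data from evaluable subjects will be included in the efficacy analysis; no imputation for missing values will be performed".

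Protocol 11.1 treats evaluability as a status to be decided and gives its timing but no criteria: "The final subject evaluability will be determined prior to breaking the code for masked lens care sequence assignment".

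The analysis populations are defined separately.

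- Protocol 11.2.2: "The FAS is the set of all randomized subjects who are exposed to at least one of the study lens care products". SAP 2.2 defines the FAS in the same way.
- Protocol 11.4: "All efficacy evaluations will use the FAS as the primary analysis set". SAP 2.2 agrees: "FAS will serve as the primary analysis dataset for all efficacy evaluations". The Synopsis and the opening of SAP Section 4 repeat this.
- Per-protocol (PP) set, Protocol 11.2.3: "excludes all data/subjects which have met any of the critical deviation criteria identified in the DEP".
- PP set, SAP 2.3: "excludes all data/subjects which have met any of the critical deviation or evaluability criteria identified in the Deviations and Evaluability Plan".

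The Deviations and Evaluability Plan (DEP), which holds the criteria, is a separate document and is not among those reviewed.

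**The concern.** The FAS depends only on randomization and exposure, while evaluability is judged later, during the study. If evaluability were a condition for entering the efficacy analysis, the primary test would run on a subset of the FAS. Because SAP 2.3 uses evaluability criteria to form the PP set, that subset could look much like the PP population.

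That would matter in this trial. Success rests on one superiority comparison. Subjects are masked only to the brand of the test solution, so they can tell a peroxide system from their own multipurpose solution, and deviations could depend on the product in use. Deciding evaluability before the code is broken limits selection on outcome, but it does not make exclusions independent of product. The question would be which subjects the estimate describes.

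The two PP definitions also differ: the SAP adds evaluability criteria to the critical deviations that the protocol names.

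**Working it through.** **What each passage does**

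1. *Protocol 11.5 and Synopsis.* Both sentences say that data from one group will be included. Neither says that only this group counts, and including one group does not exclude the others. In 11.5 the sentence covers eyes as well as subjects, although CLDEQ-8 yields one score per subject (Protocol 11.4.1), and it refers to the analysis in general. It reads as generic text in a section whose working content is that nothing is imputed.
2. *Protocol 11.2.2 and SAP 2.2.* These are the places where the population is defined. The FAS requires randomization and exposure, and nothing else.
3. *Protocol 11.4, SAP 2.2, SAP Section 4 and Synopsis.* All four name the FAS as primary for efficacy. In the Synopsis this statement comes directly before the sentence on evaluable subjects.
4. *SAP 2.3.* This is the only visible text that uses evaluability to exclude anyone, and it does so for the PP set. SAP 2.2 attaches no such criterion to the FAS.

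Read together, the passages give one answer: evaluability shapes the PP set, and the primary test uses the FAS.

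**Is power at stake?**

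Inputs (Protocol 11.10, SAP Section 7): SD of paired differences 10, difference 3, one-sided alpha 0.05, 36 per sequence. Protocol Section 8 gives about 120 randomized and about 110 completed.

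The plan's own figure comes first.

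- Normal approximation: N = [10 × (1.645 + 0.842) / 3]² = 68.7, so 69 in total.
- Noncentral t with N − 2 degrees of freedom and noncentrality 3√N/10: the smallest N with 80% power is 71, which rounds up to 72, or 36 per sequence. The stated size is reproduced, with 80.9% power at N = 72.

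The same formula at other sizes gives:

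| N analysed | Noncentrality 3√N/10 | Power |
|---|---|---|
| 72 | 2.55 | 80.9% |
| 100 | 3.00 | 90.9% |
| 110 | 3.15 | 93.1% |
| 120 | 3.29 | 94.8% |

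At a true difference of 3, the analysed set would have to fall below 71 before power dropped under 80%.

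**Could the estimate move?**

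The documents do not give the number of non-evaluable subjects. The difference between 120 and 110 is expected non-completion (10/120 = 8.3%), which is a different quantity.

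Purely as an assumption, suppose 6, 11 or 16 of 110 subjects (about 5% to 15%) were non-evaluable with no product difference, and the rest had a difference of −3.0.

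- FAS estimate: −3 × 104/110 = −2.84; −3 × 99/110 = −2.70; −3 × 94/110 = −2.56.
- Gap from −3.0: 0.16, 0.30 and 0.44 points.
- Standard error: 10/√110 = 0.95, so the gap is 0.17 to 0.46 standard errors.

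If the non-evaluable subjects had the same difference as the rest, the gap would be zero. Both the fractions and the zero effect are invented for this example, and the gap arises only under a reading that the plan does not support. The example is not evidence that the result would be distorted.

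**The case for a change.** The strongest case for a change is that a rule should mean what it says. If 'evaluable' excludes nobody, the word does nothing; if it excludes somebody, it conflicts with the FAS. Naming the FAS elsewhere does not state which rule prevails, and one sentence would settle it at almost no cost. The DEP may define the term but might not say whether it applies to the FAS. The SAP's visible text does not repeat the rule, but parts of SAP Section 4 are blacked out, so its absence there proves nothing.

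Some of this stands. The term is undefined in the visible text, the wording is careless, and the PP definitions do not match.

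The step to exclusion does not stand. It has to be inferred from a sentence that does not exclude anyone, against repeated and explicit statements of the primary set. The redactions also work against the concern: they follow directly after the FAS statements in Protocol 11.4 and SAP Section 4, so it cannot be said that nothing in the plan settles the matter.

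The bias argument is weaker here than in a parallel-group trial. In this two-period crossover, dropping a whole subject removes that subject's data on both products. Which subjects are represented would change, but one product would not lose data relative to the other. This does not cover removal of a single period, which the SAP's PP wording allows for the PP set.

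The PP mismatch concerns a set that is not primary, and both definitions refer to the same plan for their criteria.

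**Conclusion.** No change to the plan follows. The wording is a clerical looseness that an analyst resolves from the population definitions: the primary CLDEQ-8 model is fitted to the FAS with all available Day 30 scores, and evaluability criteria act on the PP set. Rewording would describe the analysis already specified, so the primary estimate, confidence limit and power would stay the same.

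This conclusion rests on two things: the explicit population statements in both documents govern over a general sentence in a missing-data section, and the unseen DEP does not itself apply evaluability criteria to the FAS. Nothing visible suggests that it does. No numerical effect can be derived, because the number of non-evaluable subjects is not stated. The difference between the two PP definitions is real but minor and does not touch the primary test.

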11.7 Safety Analysis

The safety endpoints for this study are AEs, biomicroscopy findings, and device deficiencies.

Descriptive summaries (counts and percentages) for ocular and nonocular AEs will be presented by Medical Dictionary for Regulatory Activities (MedDRA) Preferred Terms. In addition to an overall presentation of AEs, reports will be generated for serious AEs. AEs leading to study discontinuation will be identified. Individual subject listings will be provided, as necessary.

Individual subject listings will be provided for AEs that occur after signing informed consent but prior to exposure to study lens care solutions.

Each biomicroscopy parameter will be tabulated by its grade. For each biomicroscopy parameter, counts and percentages of eyes that experience an increase of ≥ 2 grades from baseline to any subsequent visit will be presented. Baseline is defined as Visit 1. A supportive listing will be generated which will include all biomicroscopy data from the affected visit for those eyes experiencing the increase of ≥ 2 grades, with the following variables: lens care solution, Investigator, subject, age, sex, visit, eye, parameter, baseline value, and value at the visit.

Two listings (prior to exposure of investigational products, and treatment-emergent) of device deficiencies, as recorded on the device deficiency Form, will be provided. Additionally, each device deficiencies category will be tabulated.

No inferential testing will be done for safety analysis.

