2 OVERVIEW OF STUDY PLAN

	Visit 1	Visit 2	Visit 3	USV
Procedure/Assessment	Screening & Baseline Period 1/Day 1	Period 1 Day 30 ± 3 Follow-Up Period 2/Day 1	Period 2 Day 30 ± 3 Follow-Up /Exit	Unscheduled Visit
Pre-Screening questionnaire (symptomatology, digital device use, and HMPS identification) ^a	X (before consent)			
Informed consent	X			
Collect demographics and activities	X			
Medical and lens/lens care history	X			
Concomitant medications/ changes in concomitant medications	X	X	X	X
Subjective (manifest) refraction ^a	X	(X)	(X)	(X)
BCVA ^a	X	(X)	(X)	(X)
Inclusion/exclusion	X			
Randomization	X			
Dispense a new pair of habitual lenses and assign/dispense the study lens care solution per randomization. Educate on instructions for use.	X	X		(X)
Snellen VA with lenses	X ^b	X ^{b, d}	X ^d	(X)
Biomicroscopy	X	X	X	X
CLDEQ-8 Questionnaire	X ^c	X	X	

	Visit 1	Visit 2	Visit 3	USV
Procedure/Assessment	Screening & Baseline Period 1/Day 1	Period 1 Day 30 ± 3 Follow-Up Period 2/Day 1	Period 2 Day 30 ± 3 Follow-Up /Exit	Unscheduled Visit
Assess AEs	X ^e	X	X	
Assess device deficiencies	X	X	X	X
Document wear time compliance (days, hours) and lens care compliance ^a		X	X	(X)
Exit form	(X)	(X)	X	(X)

^aSource only^bWith new lenses being dispensed at the visit^cBased on habitual regimen^dWith lenses worn for the study period.^eAEs are collected from the time of informed consent.

(X)= as needed.

AEs=adverse events, BCVA=best corrected visual acuity, CLDEQ-8=Contact Lens Dry Eye Questionnaire-8,

HMPS=Habitual multi-purpose solution, IRB=Institutional review board, USV=unscheduled visit, VA=visual acuity

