11	Unmasked coordinator to assign/dispense the study lens care solution for Period 1 per randomization scheme. 
1) HMPS purchased by the subject or provided by the site –or-2) Investigational Masked CCP Kit with Kit # and B&L Sensitive Eyes Saline. Educate on instructions for use and emphasize for the first-time hydrogen peroxide CLC users the warnings and use of the correct lens case with the product.
12	Assess and record any adverse events (AEs) that are reported or observed from the time of informed consent (see Section 12).
13	Record any device deficiencies that are observed or reported.
14	Schedule Visit 2 (Period 1 Follow-up) to take place on Day 30 ± 3 days (scheduled 29 (± 3) days after Visit 1. Provide subject with Visit 2 reminder instructions: 
• The subject should bring the used lens case for the study period, along with their dispensed study solution used during the study period.

10.2.2 VISIT 2 – PERIOD 1/Day 30 & PERIOD 2/DAY 1

1	Document wear time compliance (days, hours) and lens care compliance. Collect used study lens care product(s) from the subject.
2	Obtain information on any changes in medical health and/or the use of concomitant medications since Visit 1.
3	Have subject complete the Subjective Questionnaire based on lenses worn and study solution used during the 30 day study period (CLDEQ-8, [REDACTED] [REDACTED] [REDACTED])
4	Conduct Snellen VA with worn lenses. For details refer to MOP.
5	[REDACTED]

6	Remove lenses and perform biomicroscopy assessments using slit-lamp examination scales. For details and order of staining procedures, refer to MOP. Perform subjective (manifest) refraction assessment and BCVA assessment (as needed). For details refer to MOP.
7	Assess and record AEs that are observed or reported (See Section 12).
8	Record any device deficiencies that are observed or reported.
9	Dispense a new pair of habitual lenses and perform Snellen VA with new lenses being dispensed at the visit. For details refer to MOP. For two-week replacement lens wearers, provide the subject an extra pair of study lenses for replacement at two weeks. Contact the subject at approximately 15±1 days of the study period to remind the subject to replace their lenses and document date of replacement in the source.

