1.2 Study Description

This is a prospective, randomized, crossover (2-treatment, 2-period), stratified (BIOTRUE and other HMPS), observer-masked, and quasi-subject-masked study. The study population will consist of approximately 120 subjects (approximately 8 to 20 subjects per site) to be randomized at approximately 9 United States sites to achieve approximately 110 subjects completed. The expected duration of subject participation in the study (3 scheduled visits) is 30 ± 3 days per study period (up to 66 days total). Upon completing Pre-screening Questionnaire and satisfying the relevant pre-screening criteria, subjects will sign informed consent and then be considered enrolled into the study. Subjects will be randomized at Visit1, after inclusion and exclusion criteria are confirmed. The randomization will be stratified by HMPS (BIOTRUE vs. Other MPS).

Each subject will wear their habitual lens brand (following manufacture recommended replacement) on a daily wear basis for 30 ± 3 days using either CCP or their habitual solution daily to care for their lenses.

The planned visit schedule is depicted in Figure 1.2.-1.

Figure 1.2-1 Flow Diagram of Study

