2.1 Safety Analysis Set

The safety analysis set will include all subjects/eyes exposed to the newly dispensed habitual lenses for the study disinfected with at least one study lens product evaluated in this study. Safety analysis will be conducted using the safety analysis set on a treatment-emergent basis. For treatment-emergent safety analysis, subjects/eyes will be categorized under the actual lens care products exposed.

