5.3.2 Biomicroscopy Findings

Baseline is defined to be Visit 1. Each biomicroscopy parameter will be tabulated by its grade, at Baseline and Day 30. A shift table showing grade at baseline relative to Day 30 will also be presented for each parameter. For each biomicroscopy parameter, counts and percentages of eyes that experience an increase of ≥ 2 grades from baseline to any subsequent visit will be presented. A supportive listing will be generated which will include all biomicroscopy data from the affected visit for these eyes experiencing the increase of ≥ 2 grades, with the following variables: lens care solution, Investigator, subject, age, sex, visit, eye, parameter, baseline value, and value at the visit.

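### Biomicroscopy change is measured from Visit 1 in both crossover periods, so in tables split by product an increase that persists from Period 1 would appear under both products

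*Protocol*

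**What the plan says.** Both documents use a single reference examination. Protocol 11.7 says "Baseline is defined as Visit 1" and SAP 5.3.2 says "Baseline is defined to be Visit 1". The rule in Protocol 11.7 is that "counts and percentages of eyes that experience an increase of ≥ 2 grades from baseline to any subsequent visit will be presented". SAP 5.3.2 repeats it and adds a shift table from baseline to Day 30.

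Safety data follow the product used. In the treatment-emergent analyses, "subjects/eyes will be categorized under the actual lens care product exposed" (Protocol 11.2.1), and SAP 2.1 has the same rule. The supportive listing in both documents includes the lens care solution.

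The design is a two-treatment, two-period crossover with no interval between periods. The Protocol 10.2.2 heading is "VISIT 2 – PERIOD 1/Day 30 & PERIOD 2/DAY 1", and the schedule in Protocol section 2 labels the same visit "Follow-Up Period 2/Day 1".

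Neither document defines a Period 2 reference grade, a new-onset condition, or a way to treat a finding already present when Period 2 starts. Safety is descriptive, with no inferential testing (Protocol 11.7) and no safety hypotheses (SAP 5.2).

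**The concern.** At Visit 3 the difference from Visit 1 is the net change over both periods, yet under the attribution rule the eye belongs to the Period 2 product. A finding that arose on one solution and did not resolve would then be tabulated once for each solution.

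Biomicroscopy is one of three safety endpoints. Because safety is descriptive, no model with a period term adjusts for this, and the tables are the result that a reader compares. If persistent findings enter both columns, both rates rise and the columns move closer together. For a safety comparison, a shift toward no difference is the less cautious direction.

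**Working it through.** No figure in the plan depends on this rule, so there is nothing to reproduce. The check traces the rule through the visits and then sizes the effect under assumed rates.

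**Inputs from the documents**
- Baseline: Visit 1 (Protocol 11.7, SAP 5.3.2).
- Attribution: product actually used (Protocol 11.2.1, SAP 2.1).
- Order at Visit 2 (Protocol 10.2.2): slit-lamp examination at step 6, new lenses at step 9, Period 2 solution at step 10. A grade taken before Period 2 exposure therefore exists.
- Completers: 110 (Protocol synopsis), with both eyes in lenses because single-lens wearers are excluded. That gives 110 × 2 = 220 eyes per product.

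**Tracing single eyes** (product A in Period 1, product B in Period 2)

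| Eye | Visit 1 | Visit 2 | Visit 3 | Change from Visit 1 at Visits 2 and 3 | Change within Period 2 | Counted under |
|---|---|---|---|---|---|---|
| 1 | 0 | 2 | 2 | +2, +2 | 0 | A and B |
| 2 | 0 | 1 | 2 | +1, +2 | +1 | B |
| 3 | 2 | 0 | 2 | −2, 0 | +2 | neither |

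Eye 1 is the case at issue. Eye 2 shows why Visit 2 should not replace Visit 1: measured period by period, it would never be flagged. Eye 3 is possible because the Visit 1 exclusion starts at grade 3. Its two-grade rise in Period 2 is in neither the count nor the listing.

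**Size (assumed rates)**

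Let p and q be the per-period probabilities of a new increase of 2 or more grades on CCP and HMPS. Let r be the probability that a Period 1 increase is still present at Visit 3, the same for both products. Sequences are equal in size and all eyes complete both periods. Half of each product's eyes are observed in Period 2, so:

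- CCP shown = p + 0.5·q·r·(1 − p)
- HMPS shown = q + 0.5·p·r·(1 − q)
- Difference shown = (p − q) + 0.5·r·(q − p) = (p − q)(1 − r/2)

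With p = 5% and q = 2% (true difference 3.0 points; 11.0 and 4.4 eyes of 220):

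| r | CCP shown | HMPS shown | Difference (points) | Eyes, CCP and HMPS |
|---|---|---|---|---|
| 0 | 5.00% | 2.00% | 3.00 | 11.0 and 4.4 |
| 0.25 | 5.24% | 2.61% | 2.63 | 11.5 and 5.7 |
| 0.5 | 5.48% | 3.23% | 2.25 | 12.0 and 7.1 |
| 1 | 5.95% | 4.45% | 1.50 | 13.1 and 9.8 |

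With p = q = 5% there is no difference to distort, but both rates rise, to 5.6% at r = 0.25 and 7.4% at r = 1.

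**Dependence on a common r.** If only CCP-onset increases persisted (r = 1 for CCP, 0 for HMPS), then p = 5% and q = 2% would give CCP 5.00% and HMPS 2 + 0.5 × 5 × 0.98 = 4.45%, a difference of 0.55. With p = q = 5%, HMPS would show 5 + 0.5 × 5 × 0.95 = 7.38% against 5.00%. The limit of one half, with no reversal, therefore holds only for equal persistence.

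**The case against.** The case for leaving the plan alone is substantial.

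- **The split by product is inferred.** Neither section states that the table has product columns. An increase at any later visit could be read as one count per eye over the whole study, which cannot double count. This stands, and it is why the point is conditional. The attribution rule and the product variable in the listing still make the split the likelier reading, and an unsplit count would say nothing about CCP versus HMPS.
- **The count is correct for its label.** It is presented as change from Visit 1, consistently in both documents. This stands. A reader might infer that the plan, followed as written, produces wrong counts by product. The documents do not support that, because no planned table claims to count new onsets in Period 2.
- **The listing already exposes these eyes.** An eye that meets the rule at both visits is listed at both, with grade and product. This stands for eye 1 in the tracing. The listing covers affected visits only, so it gives no Visit 2 grade for eye 2 and omits eye 3.
- **Persistence need not be carry-over.** Visit 3 follows about 30 days on the other solution with new lenses, and that solution may be what sustains the finding. This stands, and it argues against replacing the Visit 1 baseline.
- **The size is hypothetical and little depends on it.** Subjects withdrawn in Period 1 cannot be counted twice. Clinically relevant worsening is also reported as an adverse event (Protocol 12.2). Study success rests on CLDEQ-8 alone. All of this stands.

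**Conclusion.** The point holds in conditional form. If the grade-increase counts and shift tables are presented by product, an increase from Period 1 that is still present at Visit 3 appears under both products. With equal persistence r, the between-product difference is multiplied by 1 − r/2; under the assumed 5% and 2%, 3.0 points becomes 2.25 at r = 0.5 and 1.5 at r = 1. If nothing persists to Visit 3, there is no effect.

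The onset rates, the persistence and its equality across products are all assumptions, since the documents supply none of them. A reader might go further and infer that the plan hides a safety difference between CCP and HMPS. That is not supported: nothing shows that such a difference exists or that findings persist, and the listing would reveal eyes affected at both visits. The primary efficacy analysis is untouched and no decision rule uses these counts. What remains is a gap in descriptive reporting: the planned tables do not show change within Period 2, and the listing supplies it only in part.

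**What to change.** In Protocol 11.7 and SAP 5.3.2:

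1. Keep the Visit 1 counts and shift tables. State whether they are split by product, and that they show change from the pre-study state.
2. For Period 2, add a supplementary count of eyes with an increase of 2 or more grades from Visit 2 to Visit 3, and a shift table over the same interval, by product.
3. In the listing, add the Visit 2 grade to Period 2 records and flag eyes already raised at Visit 2. Include eyes that meet only the supplementary rule.

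The cost is one count, one shift table and a listing column with its flag, all from examinations already scheduled. Protocol section 11 allows analysis changes by amendment or in the study report; the addition is best specified before the sequence code is broken. The Visit 2 reference should supplement Visit 1 and not replace it, because on its own it could under-report sustained findings and gradual worsening across both periods.
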